Appendix I. Richmond Agitation Sedation Scale (RASS)

Richmond Agitation-Sedation Scale (RASS)

Score	Term	Description	
+4	Combative	Overtly combative, violent, immediate danger to staff	
+3	Very agitated	Pulls or removes tube(s) or catheter(s), aggressive	
+2	Agitated	Frequent nonpurposeful movement, fights ventilator	
+1	Restless	Anxious but movements not aggressively vigorous	
0	Alert and calm		
-1	Drowsy	Not fully alert but has sustained awakening (eye opening/eye contact) to voice (≥ 10 seconds)	Verbal Stimulation
-2	Light sedation	Briefly awakens to voice with eye contact (< 10 seconds)	
-3	Moderate sedation	Movement or eye opening to voice (but no eye contact)	
-4	Deep sedation	No response to voice but movement or eye opening to physical stimulation	Physical Stimulation
-5	Unarousable	No response to voice or physical stimulation	

Appendix II. Monte Carlo simulation results of Bayesian power

1. Primary outcome of ordinal mRS at 90 days

Based on data from 3 previous trials, we assumed rates of 10%, 14%, 11%, 19%, 18%, and 28% for mRS outcome categories of (0, 1, 2, 3, 4, 5+6) for Conscious Sedation group. Data from ANSTROKE trial was downweighted 50%. We assumed a treatment effect size corresponding to an OR=1.53 (GA group having better outcomes). We simulated 10,000 trials for two total sample sizes, N=265 and N=250 and assuming rates of follow-up of 100%, 98%, 97%, 95%, and 90%. We calculated power (Table 1) to declare benefit based on range of thresholds to declare effectiveness (i.e., $\Pr(\text{OR}>1)>\text{threshold}$). For analyses, we used a neutral prior centered at OR of 1.0 (95% CI: 0.3–3.0) for the treatment effect and ordinal logistic analysis detailed in Section 9.2. Assumed cross-over rate of CS group to GA group is 10%. Type I error rates are given in Table 2.

Table 1: Power under a neutral prior and cross-over rate of 10%.

$\Pr(\text{OR}>1)>$	N=265	N=260	N=257	N=250	N=245	N=242	N=238	N=225
0.95	0.50	0.49	0.49	0.48	0.47	0.47	0.46	0.44
0.90	0.66	0.64	0.64	0.64	0.63	0.62	0.62	0.60
0.85	0.74	0.73	0.73	0.73	0.72	0.72	0.71	0.70
0.80	0.81	0.80	0.80	0.80	0.79	0.79	0.78	0.77
0.75	0.85	0.85	0.84	0.85	0.84	0.83	0.83	0.82

Table 2: Type I error rates under a neutral prior and cross-over rate of 10%.

$\Pr(\text{OR}>1)>$	N=265	N=260	N=257	N=250	N=245	N=242	N=238	N=225
0.95	0.04	0.04	0.04	0.03	0.04	0.04	0.04	0.04
0.90	0.08	0.08	0.08	0.08	0.08	0.08	0.09	0.08
0.85	0.13	0.13	0.13	0.13	0.13	0.13	0.14	0.13
0.80	0.18	0.18	0.18	0.18	0.18	0.18	0.18	0.18
0.75	0.23	0.23	0.23	0.23	0.23	0.23	0.23	0.24

2. Secondary outcome of dichotomized mRS at 90 days

We assumed good outcome (mRS of 0-2) rates of 45% for General Anesthesia group and 35% for Conscious Sedation group. We simulated 10,000 trials for each of the sample sizes in Table 3 and calculated power to declare benefit based on range of thresholds to declare benefit (i.e., $\Pr(\text{RR}>1)>\text{threshold}$). For analyses, we used a neutral prior centered at RR of 1.0 (95% CI: 0.3–3.0) for the treatment effect and a log binomial model detailed in section 9.2.

Table 3: Power under a neutral prior and cross-over rate of 10%.

$\Pr(\text{RR}>1)>$	N=265	N=260	N=250	N=242	N=225
0.95	0.42	0.43	0.42	0.37	0.41
0.90	0.58	0.57	0.56	0.54	0.56
0.85	0.67	0.67	0.66	0.62	0.64
0.80	0.73	0.74	0.73	0.71	0.72
0.75	0.79	0.79	0.77	0.76	0.77

To compute type I error, we assumed equal rates of good outcomes of 35% for both groups. We used the same neutral prior (RR of 1.0, 95% CI, 0.3–3.0) and log binomial model for analysis. Type I error rates are given in Table 4.

Table 4: Type I error rates under a neutral prior and cross-over rate of 10%.					
Pr(RR>1)>	N=265	N=260	N=250	N=242	N=225
0.95	0.05	0.04	0.04	0.05	0.04
0.90	0.09	0.09	0.08	0.09	0.08
0.85	0.14	0.14	0.14	0.15	0.12
0.80	0.19	0.21	0.19	0.19	0.17
0.75	0.24	0.25	0.23	0.24	0.24

We also computed the power under a skeptical prior expressing prior belief that Conscious Sedation will have higher rates of good outcome. Using a skeptical prior centered at RR of 0.82 (95% CI: 0.27–2.5) for the analyses gives power shown in Table 5. Here, there will be >50% power to convince a skeptic of benefit of General Anesthesia (RR>1) using a posterior probability threshold of 90% or lower.

Table 5: Power under a skeptical prior and cross-over rate of 10%.					
Pr(RR>1)>	N=265	N=260	N=250	N=242	N=225
0.95	0.37	0.40	0.37	0.40	0.34
0.90	0.52	0.56	0.53	0.53	0.50
0.85	0.62	0.65	0.61	0.63	0.58
0.80	0.70	0.73	0.70	0.71	0.65
0.75	0.76	0.78	0.75	0.77	0.71

Appendix III. Prudent limits of targeted depth and length of ED procedural sedation and analgesia according to presedation assessment of aspiration risk

Standard-risk patient ^a		Procedural Urgency ^b				Procedural sedation and analgesia targeted depth and duration ^c
Oral intake in the prior 3 hours		Emergent Procedure	Urgent Procedure	Semi-Urgent	Non-Urgent	
Nothing	All levels of sedation	All levels of sedation	All levels of sedation	All levels of sedation	All levels of sedation	
Clear liquids only	All levels of sedation	All levels of sedation	Up to and including brief deep sedation	Up to and including extended moderate sedation		
Light snack	All levels of sedation	Up to and including brief deep sedation	Up to and including dissociative sedation; non-extended moderate sedation	Minimal sedation only		
Heavier snack or meal	All levels of sedation	Up to and including extended moderate sedation	Minimal sedation only	Minimal sedation only		
Higher-risk patient ^a		Procedural Urgency ^b				
Oral intake in the prior 3 hours		Emergent Procedure	Urgent Procedure	Semi-Urgent	Non-Urgent	
Nothing	All levels of sedation	All levels of sedation	All levels of sedation	All levels of sedation	All levels of sedation	
Clear liquids only	All levels of sedation	Up to and including brief deep sedation	Up to and including extended moderate sedation	Minimal sedation only		
Light snack	All levels of sedation	Up to and including dissociative sedation; non-extended moderate sedation	Minimal sedation only	Minimal sedation only		
Heavier snack or meal	All levels of sedation	Up to and including dissociative sedation; non-extended moderate sedation	Minimal sedation only	Minimal sedation only		

↓ Increasing potential aspiration risk

Brief: <10 minutes
Intermediate: 10-20 minutes
Extended: >20 minutes

Figure. Prudent limits of targeted depth and length of ED procedural sedation and analgesia according to presedation assessment of aspiration risk

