9.2 Statistical Analyses

Intent-to-treat analyses will be performed. To summarize the data, descriptive statistics will be used. Demographics, vital signs, laboratory variables, stroke type and duration from onset of symptoms will be summarized for each treatment arm. Vital signs taken during the treatment period will be displayed graphically. In addition to ICH, other medical events will be tabulated by body system and severity.

Primary analyses will focus on comparing GA (combining inhalational and IV anesthesia) to sedation. All analyses will be conducted under a Bayesian paradigm to obtain estimates of odds ratio (OR) for primary outcome (ordinal mRS), relative risk (RR) for binary outcomes, and probability of treatment benefit or harm (quantities that cannot be obtained from frequentist analyses). For the treatment effect, we will use a neutral prior centered at OR of 1.0 with 95% prior interval of 0.3-3.0. This prior assumes a priori equipoise and excludes large treatment effects. Weakly informative priors will be used for all other parameters to exclude large treatment effects.²⁴

Generalized linear mixed models will be used to analyze all outcomes and will include treatment group, terminal ICA occlusion and time from onset of symptoms (stratification variables) as covariates and center (stratification variable) as a random effect to account for center variability. For the primary outcome of ordinal mRS at 3 months (scores 5 and 6 combined), we will use an ordinal logistic model. For binary outcomes we will use log binomial (or logistic in case of non-convergence) models to directly estimate relative risks (or odds ratios) and 95% CIs. The prior for the treatment effect will be a Normal (0, $sd=0.57$) in the log OR/RR scale. The prior for the intercept will be Normal (0, $sd=10$) and Normal (0,1) for other covariates in the model. A half-Normal(0,1) prior will be used for the standard deviation of the center random effect. For non-binary outcomes, we will select the best fitting models and use neutral, weakly informative priors that exclude large treatment effects. We will examine residuals from each model to ensure reasonable adherence to the assumptions of the models.

If, despite randomization with stratification for center, tICA, and time from onset of symptoms, any important differences between intervention groups occur in baseline variables related to outcome, secondary analyses will be performed controlling for these factors.

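### Several power and type I error figures in Appendix II Tables 3-5 (dichotomized mRS) differ from each other and from recomputed values by more than 10,000 simulated trials allow

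*Combined protocol and SAP*

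**What the plan says.** Part 2 of Appendix II covers the secondary outcome of mRS 0-2 at 90 days.

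- **Scenario.** "We assumed good outcome (mRS of 0-2) rates of 45% for General Anesthesia group and 35% for Conscious Sedation group". Part 1 adds "Assumed cross-over rate of CS group to GA group is 10" percent, and the captions of Tables 3-5 repeat the 10% cross-over. For type I error both arms are set at 35%.
- **Runs.** "We simulated 10,000 trials for each of the sample sizes in Table 3 and calculated power to declare benefit". For the other two tables the text says only "Type I error rates are given in Table 4" and that the skeptical prior "gives power shown in Table 5".
- **Neutral prior (Tables 3 and 4).** "we used a neutral prior centered at RR of 1.0 (95% CI: 0.3–3.0) for the treatment effect and a log binomial model". Section 9.2 fixes the scale: "The prior for the treatment effect will be a Normal (0, $sd=0.57$) in the log OR/RR scale".
- **Skeptical prior (Table 5).** Centered at RR 0.82 with 95% interval 0.27-2.5.
- **Conclusion drawn.** Power to convince a skeptic is above 50% at any posterior threshold of 90% or lower. The sentence names no sample size.

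**The concern.** Power should fall slowly and smoothly as N falls, apart from small steps caused by discrete counts. A prior shifted toward sedation, with practically the same spread, cannot raise Pr(RR>1) on the same data. Tables 3-5 break both patterns in places, and the printed gaps are several times the simulation error that 10,000 runs would leave. Tables 1 and 2, for the ordinal primary outcome, are almost smooth in N, so the disorder is confined to part 2.

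At stake are the stated operating characteristics of a named secondary outcome and the statement about persuading a skeptic. At the planned N=260, Table 5 prints 0.56 at threshold 0.90, a more comfortable margin over one half than the assumptions give.

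**Working it through.** **1. Printed cells against each other, with no model.** SE of a difference = sqrt[p1(1-p1)/10000 + p2(1-p2)/10000]. Worst-case rounding removes 0.01 from each gap.

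| Comparison | Printed | SE of difference | Gap in SE | After rounding |
|---|---|---|---|---|
| Table 3, 0.95: N=225 vs N=242 | 0.41 vs 0.37 | 0.0069 | 5.8 | 4.4 |
| Table 5, 0.90: N=260 vs N=265 | 0.56 vs 0.52 | 0.0070 | 5.7 | 4.3 |
| Table 4, 0.80: N=260 vs N=225 | 0.21 vs 0.17 | 0.0055 | 7.2 | 5.4 |
| N=242, 0.95: Table 5 vs Table 3 | 0.40 vs 0.37 | 0.0069 | 4.4 | 2.9 |

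Table 3 rises at all five thresholds between N=242 and N=225. Table 5 at N=260 exceeds N=265 by 2-4 points at all five (3.4 to 5.7 SE before rounding). Rows within a column presumably come from the same simulated trials, so they are not independent confirmations.

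**2. Model.** Inputs from Appendix II: pG = 0.45; pC = 0.9 × 0.35 + 0.1 × 0.45 = 0.36; n = N/2 per arm. Neutral prior on log RR: m = 0, s = 0.57 (section 9.2). Skeptical prior: m = ln 0.82 = -0.198, s = ln(2.5/0.27)/(2 × 1.96) = 0.568. With a normal approximation for log RR:

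- V = (1-pG)/(n pG) + (1-pC)/(n pC)
- benefit is declared when the estimated log RR exceeds c = V[z sqrt(1/V + 1/s²) - m/s²], where z is the normal quantile of the threshold
- power = 1 - Φ[(c - ln(pG/pC))/√V], with ln(0.45/0.36) = 0.2231

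**3. Reproducing printed columns first** (thresholds 0.95 to 0.75).

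- Table 5, N=265: 0.378/0.526/0.625/0.698/0.756, printed 0.37/0.52/0.62/0.70/0.76. Agreement within 1 point.
- Table 3, N=260: 0.408/0.557/0.654/0.725/0.780, printed 0.43/0.57/0.67/0.74/0.79. Agreement within about 2 points.

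**4. Columns that do not reproduce.**

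- *Table 5, N=260, threshold 0.90.* V = 0.55/58.5 + 0.64/46.8 = 0.02308, √V = 0.1519. c = 0.02308 × [1.2816 × sqrt(43.33 + 3.10) + 0.615] = 0.2157. Power = 1 - Φ[(0.2157 - 0.2231)/0.1519] = 1 - Φ(-0.049) = 0.519, printed 0.56. All rows: 0.372/0.519/0.619/0.693/0.751, printed 0.40/0.56/0.65/0.73/0.78. Excess 2.8/4.1/3.1/3.7/2.9 points.
- *Table 3, N=225, threshold 0.95.* n = 112.5, V = 0.02667, √V = 0.1633. c = 0.02667 × 1.6449 × sqrt(37.5 + 3.08) = 0.2794. Power = 1 - Φ(0.345) = 0.365, printed 0.41.
- *Table 4, threshold 0.80* (0.35 in both arms). 0.190 at N=260 and 0.189 at N=225, printed 0.21 and 0.17.
- *N=242, threshold 0.95.* Neutral 0.386, skeptical 0.349, an expected gap of -3.7 points. The printed gap is +3.

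**5. Exact check.** Full enumeration of binomial outcomes with a grid log-binomial posterior gives, for Table 5 at 130/130, 0.363/0.511/0.611/0.703/0.746. Averaged over modestly unequal splits of 260 it gives 0.378/0.526/0.625/0.697/0.756, so the printed excess becomes 2.2/3.4/2.5/3.3/2.4 points. For Table 3 at N=225, threshold 0.95, near-equal splits give 0.355-0.371, and about 0.38 is the most within a few patients of equal. For Table 4 at threshold 0.80, near-equal splits give 0.199 (N=260) and 0.195-0.197 (N=225).

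**6. The skeptic sentence at threshold 0.90.** At N=260: 0.511 (130/130), 0.519 (smooth), 0.526 (averaged splits), so above one half. At N=225: 0.473 (smooth) and 0.46-0.49 by split; Table 5 itself prints 0.50, which is not above one half.

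**The case against.** Most of the case on the other side stands as a limit on the point.

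- **Run count.** The 10,000 is tied to Table 3 only. A reader might infer that all three tables contradict a stated count; for Tables 4 and 5 it is implied, not stated.
- **Skeptical against neutral.** A reader might infer that every Table 5 cell must lie below its Table 3 cell. That is guaranteed only on shared data sets, which the documents do not claim. At N=242 the reversals at 0.85 (0.63 vs 0.62) and 0.75 (0.77 vs 0.76) are within rounding; only the one at 0.95 is substantive.
- **Arm split.** Exact power moves with the split. At 130/131 the first three Table 5 rows become 0.393/0.543/0.641, so an excess of 3-5 points holds only at exactly 130/130. The most favourable splits of 260 reach about 0.39/0.54/0.64/0.71/0.76, still below every printed value. Table 4 is the most sensitive: 0.21 against the exact 0.199 is only about 1.5 SE after rounding, and unequal splits of 225 can bring type I error down to about 0.18. Split effects do not explain 0.41 in Table 3.
- **Model.** Section 9.2 has covariates, a center random effect and a logistic fallback. No values are given for the first two, so none were modelled; they should move all columns together and not create reversals. The logistic fallback lowers Table 5 at N=260 further (0.316/0.461/0.564/0.658/0.711).
- **Direction.** A reader might infer systematic flattery. Table 4 at N=225 (0.17) and Table 3 at N=242 (0.37) are printed too low, so the documents do not support that.
- **Consequence.** No success or stopping rule uses these tables or the skeptical prior. This is correct and lowers the weight of the point.

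**Conclusion.** The point holds as a minor reporting error. Tables 3-5 contain cells that 10,000 trials under the stated assumptions would not produce. The clearest are Table 3 at N=225, threshold 0.95 (0.41 against about 0.36-0.37), and the whole N=260 column of Table 5 (about 2-4 points above roughly 0.37/0.52/0.62/0.70/0.755). The Table 4 pair at threshold 0.80 and the single substantive reversal at N=242 point the same way. Many other columns reproduce within about 2 points.

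The recomputed values assume 45% against 36%, the stated priors, near-equal arms, and no covariate or center effects; they shift by a point or two with the arm split.

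Two stronger conclusions are not supported. The cause is not shown: fewer runs would explain most of the scatter, but mislabelled columns could too (exchanging N=242 and N=225 in Table 3 would restore order there). Nor does this touch the design: section 9.1 sizes the trial on the ordinal primary outcome, and Tables 1 and 2 are not in question. The claim of more than 50% power against a skeptic survives at N=260 and threshold 0.90, at about 0.51-0.53, but not at N=225.

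**What to change.** Rerun Tables 3, 4 and 5 with 10,000 trials per sample size, applying both priors to the same simulated data sets so that Tables 3 and 5 are directly comparable. State for each table the run count, the arm sizes and whether covariates and a center effect were simulated, and check the column labels against the output. Replace the printed figures. If fewer runs were used for any table, say how many. Limit the sentence about convincing a skeptic, at threshold 0.90, to the planned N=260 and give the rerun value.

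The cost is a rerun of existing code and a revised appendix. Some power figures will drop by a few points and others will rise slightly. The sample size, primary analysis and decision rules stay as they are.
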